10.5.2 General guidelines for reporting adverse events

- Patients for whom the screening visit of this study is done at the same time as the EOS visit of the previous eliglustat study they were enrolled in, the safety follow-up phone scheduled 30-37 days after the EOS visit of the previous study will not be done. Instead, these patients will be monitored according to the standard safety procedures of this study. The Ethics Committees (and Local Health Authority, if required) at the affected sites will be notified.
- All AEs, regardless of seriousness or relationship to IMP, spanning from the signature of the informed consent form until the end of study visit, or the last IMP administration for patient with early termination, are to be recorded on the corresponding page(s) or screen(s) of the CRF.
- The following categories of medico/surgical events are considered part of the medical/surgical history of the patient and should be entered in the Medical/surgical history CRF:
 - AEs started during the previous study, which are closed at the time of the screening visit and are still considered clinically significant by the investigator at the time of the screening visit.
 - Medical/surgical events started after the follow-up phone call of the previous study and before the ICF signing in the current study, whether ongoing or closed, if they are considered clinically significant by the investigator.
- AEs started during the previous study, which are ongoing at the time of the screening visit should be entered in the AE CRF regardless of whether the patient had a gap in eliglustat

treatment after the end of the previous study, or the end of study visit of the previous study and the screening visit of this study are concomitant.

- Whenever possible, diagnosis or single syndrome should be reported instead of symptoms. The Investigator should specify the date of onset, intensity, action taken with respect to IMP, corrective treatment/therapy given, additional investigations performed, outcome, and his/her opinion as to whether there is a reasonable possibility that the AE was caused by the IMP or by the study procedure(s).
- The Investigator should take appropriate measures to follow all AEs until clinical recovery is complete and laboratory results have returned to normal, or until progression has been stabilized, or until death, in order to ensure the safety of the patients. This may imply that observations will continue beyond the last planned visit per protocol, and that additional investigations may be requested by the monitoring team up to as noticed by Genzyme. Patients who experience an ongoing SAE or an AESI at the prespecified study end-date, should be monitored until follow-up is no longer considered medically necessary or the patient is lost to follow-up.
- When treatment is prematurely discontinued, the patient's observations will continue until the end of the study visit as defined by the protocol for that patient, unless the patient is lost to follow up.
- Clinically significant laboratory abnormalities after Visit 3 (Day 1) are to be recorded as AEs only if:
 - Symptomatic and/or
 - Requiring either corrective treatment or consultation, and/or
 - Leading to IMP discontinuation or modification of dosing, and/or
 - Fulfilling a seriousness criterion, and/or
 - Defined as an AESI

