^b Study duration will be up to 4 years, or until eliglustat is approved and available to patients through reimbursement with minimum duration of 2 years. If after 4 years since the beginning of the study eliglustat is not approved and available to patients in participating country, patients in this country may continue to receive study treatment until eliglustat is available to patients through the compassionate use (expanded access) program or is approved and available through reimbursement, whichever comes first. At study completion or patient discontinuation/withdrawal certain radiological assessments will not be repeated (bone X-Ray if performed less than 2 years prior; DXA, bone MRI and liver and spleen MRI if performed less than 1 year prior).

^c A unique patient ID number will be assigned. The ID of the previous study the patient was enrolled in and the patient's ID in that study will be collected in the new clinical database.

^d Medico-surgical history already collected in the previous study database should not be re-entered. Should be entered in the Medical/surgical history CRF 1/ adverse events (AEs) started during the previous study, which are closed at the time of the screening visit and are still considered clinically significant by the investigator at the time of the screening visit; 2/ medical/surgical events started after the follow-up phone call of the previous study and before the ICF signing in the current study, whether ongoing or closed, if they are considered clinically significant by the investigator.

^e Prior medications are all ongoing medications at the time of screening, and medications received during the 30 day period prior to screening even if no longer taken at the time of screening, including eliglustat and enzyme replacement therapy (ERT).

^f Only at Study completion visit and not at Patient discontinuation/withdrawal visit.

^g Patients will be contacted approximately every 4 weeks for safety monitoring and will be asked if they have had any significant experiences, begun taking any new medications, changed the dose of any medications they are taking. In addition patients of child bearing potential will be asked about the result of the urine pregnancy test performed every 4 weeks at home.

^h Serum samples for CTX should be collected after overnight fasting.

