Overall, eliglustat shows a favorable safety profile. Based on review of all available safety data, the adverse drug reaction profile of eliglustat is characterized by diarrhea, headache, arthralgia, flatulence, abdominal pain, fatigue, and nausea, each occurring in <6% of the treated population. Most reported adverse events (AEs) were mild in severity, and few patients discontinued due to AEs. The risks of greatest concern with eliglustat treatment have not been observed in clinical trials, but modeling suggests the possibility for clinically significant electrocardiogram (ECG) interval increases, which are mild in scope, in the setting of high eliglustat exposure. Also, since eliglustat is extensively metabolized by CYP2D6 and to a lesser extent by CYP3A4, the potential for drug-drug interactions that could lead to increases in eliglustat exposure exists. CYP2D6 phenotype based dosing regimen allows managing potential for drug-drug interactions by restricting the patient population to PM, IM, and EM patients only, to ensure that patient exposure to eliglustat will remain within the therapeutic range.

As seen in the Phase 2 study, ENGAGE, and ENCORE, and commensurate with the general population, more than 90% of GD1 patients are CYP2D6 PMs, IMs, or EMs, can be safely and effectively dosed at 100 mg daily (QD) (PMs) or 100 mg BID (IMs and EMs). The sufficiency of the IM and EM proposed dose is supported in particular by the Phase 2 study and ENGAGE, where most treatment naïve patients with IM and EM phenotypes were successfully treated at the 100 mg BID dose.

While patients of all phenotypes were successfully treated in clinical trials using dose titration, Sanofi Genzyme recommends an eliglustat dosing regimen comprised of 100 mg BID for IM and EM patients and 100 mg QD for PM patients in the post approval setting.

During the clinical development program, a limited number of GD1 patients who were ultra rapid metabolizers (URMs) (1 in ENGAGE and 4 in ENCORE) were treated with eliglustat. The single URM patient in ENGAGE who received 100 mg BID was a nonresponder, suggesting that the 100 mg dose may result in a maximum concentration (C_{max}) too low to be effective for URM. For indeterminate metabolizers, a phenotype cannot be predicted based on genotype, and therefore a dose cannot be recommended. Other treatment options are available for this minority of patients who would be ineligible for treatment with eliglustat.

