8.5 CONCOMITANT MEDICATION

Patients will be monitored continuously for changes in the use of concomitant medications (introduction of new medications and changes in the dose or regimen of preexisting medications).

Patients will be instructed to report to the Investigator any changes in concomitant medications before these changes are made, or, in the case of changes made in emergency situations, as soon as possible.

8.5.1 INTERACTION WITH OTHER MEDICINAL PRODUCTS AND OTHER FORMS OF INTERACTION**8.5.1.1 ANTIARRHYTHMICS**

Because eliglustat is predicted to cause mild increases in ECG intervals (PR, QTc, and QRS) at substantially elevated eliglustat plasma concentrations, use of eliglustat is prohibited in combination with Class IA and Class III antiarrhythmic medications. Patients who require long term treatment with any of these medications should be removed from the study.

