9.2.2 Safety endpoints

9.2.2.1 Adverse events

Refer to [Section 10.5](#) to [10.7](#) for details.

Continuous monitoring will be performed for (S)AEs and concomitant medications.

Results of pregnancy testing for female patients of childbearing potential will be collected.

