10.2.3 Semiannual visits

Semiannual visits will be performed at 6 month intervals (+/-14 days) in reference to the Day 1 visit.

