### ***Analysis of all treatment-emergent adverse events***

The following treatment-emergent adverse event summaries will be generated for the safety population.

- Overview of treatment-emergent adverse events, summarizing number (%) of patients with any
  - Treatment-emergent adverse event
  - Treatment-emergent serious adverse event
  - Treatment-emergent adverse event of special interest (AESI)
  - Treatment-emergent adverse event leading to death
  - Treatment-emergent adverse event leading to permanent treatment discontinuation
  - Treatment-related treatment-emergent adverse event
  - Severe treatment-emergent adverse event
- All treatment-emergent adverse event by primary SOC, HLT, HLT, and PT, showing number (%) of patients with at least 1 treatment-emergent adverse event sorted by the SOC internationally agreed order. The other levels (HLGT, HLT, PT) will be presented in alphabetical order
- All treatment-emergent adverse events by primary SOC and PT, showing the number (%) of patients with at least 1 treatment-emergent adverse event, sorted by the internationally agreed SOC order and by decreasing incidence of PTs within each SOC. This sorting order will be applied to all other tables, unless otherwise specified
- All treatment-emergent adverse events regardless of relationship and related by primary SOC and PT, showing the number (%) of patients with at least 1 treatment-emergent adverse event, sorted by the internationally agreed SOC order and by decreasing incidence of PTs within each SOC
- All treatment-emergent adverse events by maximal severity, presented by primary SOC and PT, showing the number (%) of patients with at least 1 treatment-emergent adverse event by severity (ie, mild, moderate, or severe), sorted by the sorting order defined above

- By-patient listing of all treatment-emergent adverse events
- By-patient listing of all severe treatment-emergent adverse event

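### The four-weekly safety contact asks about undefined significant experiences, which is narrower than the duty to record all AEs, so mild untreated events may be under-ascertained

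*Protocol*

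**What the plan says.** Protocol 10.5.2 sets the recording duty: "All AEs, regardless of seriousness or relationship to IMP, spanning from the signature of the informed consent form" to the end of study visit, or to the last dose for patients who terminate early, go on the CRF.

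The flow chart (1.2) marks the AE/SAE recording row as continuous monitoring and attaches footnote g. That footnote has each patient "contacted approximately every 4 weeks for safety monitoring and will be asked if they have had any significant experiences, begun taking any new medications", and also whether any dose has changed. Patients of childbearing potential are asked for their home pregnancy test result. The word significant is not defined.

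Other sections bear on the same point:
- Protocol 9.2.2.1: "Continuous monitoring will be performed for (S)AEs and concomitant medications". It gives no method. SAP 2.1.4.1 repeats the statement, also without a method.
- Protocol 8.5: "Patients will be instructed to report to the Investigator any changes in concomitant medications before these changes are made".
- Protocol 10.2.3: "Semiannual visits will be performed at 6 month intervals (+/-14 days) in reference to the Day 1 visit". Section 10.2.3.1 lists AE as an assessment at these visits, and 10.2.5.1 lists it at completion or discontinuation. Neither gives the question to be put.
- SAP 2.4.5.1 plans a table of "All treatment-emergent adverse events by maximal severity, presented by primary SOC and PT", graded mild, moderate or severe.

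**The concern.** The recording duty covers every event, but the written between-visit prompt covers a subset that each patient defines for himself or herself. The events most likely to be screened out are minor ones, and those dominate this drug's known profile. Protocol section 4 says "Most reported adverse events (AEs) were mild in severity". It lists diarrhea, headache, arthralgia, flatulence, abdominal pain, fatigue and nausea as the characteristic reactions, each in under 6% of treated patients. Someone on the drug for some 4 to 8 years could well regard such symptoms as ordinary.

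Safety, by continuous monitoring of AEs, is a secondary objective (protocol 5.2), and the four-weekly contact is the stated means of that monitoring. Few other sources would reveal missed mild symptoms. No vital sign or ECG variables are collected (SAP 2.1.4.4 and 2.1.4.5), and serum chemistry is scheduled at screening only (SAP Table 1). At stake is whether the mild rows of the TEAE tables can be read at face value. The SAP does not say that these events may have been solicited more narrowly.

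**Working it through.** The documents state no expected TEAE incidence and no capture rate, so there is no figure to reproduce. The check has three parts.

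**1. The texts side by side.** Section 10.5.2 says what must be recorded: everything. Footnote g says what is asked between visits: significant experiences, new medications and dose changes. The general statements in protocol 9.2.2.1 and SAP 2.1.4.1 carry no restriction, but they offer no other method. Footnote g is therefore the operative text, and it is narrower than 10.5.2. The gap that remains is an event that is mild, untreated (so no medication question picks it up) and not volunteered.

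**2. The schedule.** Contacts come about every 4 weeks and visits every 26 weeks.
- Contacts per visit interval: 26 / 4 = 6.5.
- Contacts over two years: 104 / 4 = 26.
- Scheduled visits over two years: 104 / 26 = 4 (Weeks 26, 52, 78 and 104).
- Longest wait for a listed AE assessment: nominally 26 × 7 = 182 days. If one visit is 14 days early and the next 14 days late, it is 182 + 28 = 210 days.

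**3. Illustration of sensitivity.** All inputs here are assumptions, except the sample of about 32 (protocol 11.1) and the 6%, which is the upper bound quoted in protocol section 4.
- p is the true two-year patient incidence.
- m is the share of episodes that are mild, taken as 0.5 to 0.8. The protocol says only that most were.
- c is the probability that a mild episode is captured by any route, taken as 0.5 to 1.0.
- Moderate and severe episodes are assumed fully captured.

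Effective capture is e = 1 − m(1 − c). With one episode per affected patient, observed incidence is p × e. With Poisson recurrences and each patient counted once, as SAP 2.4.5.1 specifies, it is 1 − (1 − p)^e. For example, with m = 0.8 and c = 0.5, e = 1 − 0.8 × 0.5 = 0.60. For p = 30% the single-episode result is 0.30 × 0.60 = 18.0%. With m = 0.5 and c = 0.5, e = 0.75 and the recurrent result is 1 − 0.70^0.75 = 23.5%.

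| c | p = 30% (9.6 of 32) | p = 6% (1.9 of 32) | any TEAE, p = 90% (recurrent only) |
|---|---|---|---|
| 1.0 | 30% | 6% | 90% |
| 0.9 | 27.6–28.7% | 5.5–5.7% | 88.0–88.8% |
| 0.7 | 22.8–26.2% | 4.6–5.1% | 82.6–85.9% |
| 0.5 | 18.0–23.5% | 3.6–4.5% | 74.9–82.2% |

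The first two columns run from the single-episode formula with m = 0.8 to the recurrent formula with m = 0.5. The third uses the recurrent formula for both values of m. Observed incidence never exceeds the true value, and the loss is nil when c = 1. The any-TEAE row is the best protected in relative terms, because a patient needs only one captured event to be counted.

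**The case against.** The best reply is that no rule is broken. Section 10.5.2 is a recording duty, footnote g summarises a telephone-style contact, and a loose prompt does not release the site from recording whatever it learns. That is correct. This is a mismatch between a prompt and a duty, not a contradiction between two rules.

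A reader might infer that the contact covers significant experiences and nothing else. The documents do not support that: the same sentence asks about new medications and dose changes, and 8.5 requires medication changes to be reported. Treated mild events therefore have a second route about every four weeks.

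A reader might also infer that the six-monthly visit is an unfiltered enquiry. The protocol lists AE at visits but gives no wording, so this is unknown.

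The consequences are also limited. The study is single-arm with no hypothesis testing (protocol 11.4), so no contrast or decision rule is distorted. For a reaction at 6%, only about two of 32 patients are involved. Poor recall of onset dates does not lower counts either, because SAP 2.5.3 treats unclear onset as treatment-emergent by default.

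These replies narrow the point and lower its priority. They do not remove it: an untreated, unvolunteered mild symptom has no stated prompt between visits.

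**Conclusion.** Footnote g is narrower than 10.5.2, and mild TEAE incidence may be under-ascertained as a result. If anything is missed, the effect is downward. The size cannot be derived from the documents, and the table above shows only how the result moves under assumed inputs.

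A reader might go further and conclude that TEAE incidence is biased downward by a calculable fraction, for instance by multiplying an assumed mild share by an assumed recall loss. That is not supported. Neither input is given, the product assumes that the 26 or so contacts pick up no mild event at all, and it counts events where the SAP counts patients once per event. What stands is a plausible ascertainment gap, confined to mild, untreated, unvolunteered events, in a descriptive safety result. The point is low priority and worth making because the remedy is so cheap.

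**What to change.** In footnote g of protocol 1.2, replace the reference to significant experiences with an open question: whether the patient has had any new or worsened symptom, illness, injury or medical event since the last contact, whether or not he or she considers it important. Keep the medication and pregnancy test questions as they are. The prompt then matches 10.5.2.

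The cost is one phrase in the flow chart footnote and in any site material built on it. No contacts or visits are added. The downside is somewhat more minor AEs to record. If the phrase is kept, define significant and state in the SAP that mild TEAE incidence may be understated.

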- The patient experiences a decline in Gaucher disease status that, in the opinion of the Investigator, warrants discontinuation from the study (eg, repeated bone crises, clinically significant increases in liver or spleen volumes).

Patient who discontinue or withdraw from participation in the study will be contacted in order to obtain information about the reason(s) for discontinuation/withdrawal and for collection of AEs, if any. The patient will be asked to return to the clinic to complete all study discontinuation/withdrawal assessments. The Investigator will describe the reason for

discontinuation on the Completion/Discontinuation case report form. Patients who discontinue/withdraw participation from the study will not be replaced. A summary of all discontinuations will be included in the final study report.

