10.2.5 Study completion or patient discontinuation/withdrawal

10.2.5.1 Clinical assessments

- Complete physical exam including weight
- Gaucher disease clinical assessments
- SF-36
- IMP compliance.
- AE
- Concomitant medications

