10.4.3 Criteria for permanent treatment discontinuation

The patients may withdraw from treatment with the IMP if they decide to do so, at any time and irrespective of the reason, or this may be the Investigator's decision. All efforts should be made to document the reasons for treatment discontinuation and this should be documented in the e-CRF.

The use of eliglustat is prohibited in combination with Class IA and Class III antiarrhythmic medications. See [Section 8.5.1.1](#) for detail.

Patients requiring medications incompatible with eliglustat because of drug-drug interaction for longer than 2 weeks should be discontinued from the study. See [Section 8.5.1.2](#) for detail.
Handling of patients after permanent treatment discontinuation

Patients will be followed-up according to the study procedures as specified in this protocol up to the scheduled date of study completion, or up to recovery or stabilization of any AE to be followed-up, whichever comes last, unless the patient is lost to follow up.

If possible, and after the permanent discontinuation of treatment, the patients will be assessed using the procedure normally planned for the last visit at study completion or patient discontinuation/withdrawal.

All cases of permanent treatment discontinuation should be recorded by the Investigator in the appropriate pages of the CRF when considered as confirmed.

10.4.4 Procedure and consequence for patient withdrawal from study.

The patients may withdraw from the study before study completion if they decide to do so, at any time and irrespective of the reason.

If possible, the patients are assessed using the procedure normally planned for the visit at study completion or patient discontinuation/withdrawal.

For patients who fail to return to the site, the Investigator should make the best effort to recontact the patient, and to determine his/her health status, including at least his/her vital status. Attempts to contact such patients must be documented in the patient's records (eg, times and dates of attempted telephone contact, receipt for sending a registered letter).

The statistical analysis plan will specify how these patients lost to follow-up for their primary endpoints will be considered.

Patients who have withdrawn from the study cannot be enrolled again in the study. Their inclusion and treatment numbers must not be reused.

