### ***Observation period***

The observation period will be divided into 4 periods:

- The **pre-treatment period** is defined as the time from the signed informed consent to first dose of IMP administration in this study.
- The **treatment-emergent period** is defined as the time from the first administration of the IMP to the last administration of the IMP + 5 days. The treatment-emergent period includes the following 2 periods:
  - The **on-treatment period** is defined as the period from the first IMP administration to the last administration of the IMP + 1 day.
  - The **residual treatment period** is defined as the time from the last administration of IMP to the end of the treatment-emergent period.
- The **post-treatment period** is defined as the period from the end of treatment-emergent period.

The treatment-emergent adverse event (TEAE) observation period includes both on-treatment and residual treatment periods.

The on-study observation period is defined as the time from screening until the end of the study (defined as last protocol planned visit or the resolution/stabilization of all serious adverse events [SAEs] and adverse events of special interest [AESIs]).

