### ***2.1.4.1 Adverse events variables***

#### ***Adverse event observation period***

- Pre-treatment adverse events are adverse events that developed or worsened or became serious during the pre-treatment period.
- Treatment-emergent adverse events (TEAEs) are adverse events that developed or worsened or became serious during the treatment-emergent period (treatment-emergent adverse event observation period).
- Post-treatment adverse events are adverse events that developed or worsened or became serious during the post-treatment period.

Continuous monitoring will be performed for (S)AEs and concomitant medications. Results of pregnancy testing for female patients of childbearing potential will be collected. Patients with an SAE or AESI should be followed until event resolution or when follow-up is no longer considered medically necessary, or the patient is lost to follow-up.

All adverse events (including SAEs and AESIs) will be will be coded to a lower-level term (LLT), preferred term (PT), high-level term (HLT), high-level group term (HLGT), and associated primary system organ class (SOC) using the version of Medical Dictionary for Regulatory Activities (MedDRA) currently in effect at Sanofi at the time of database lock.

Adverse events (including serious adverse events and adverse event of special interest) will be recorded from the time of signed informed consent until the end of the study.

Any SAE (including death) brought to the attention of the Investigator at any time after the end of the study for the patient and considered by him/her to be caused by the IMP with a reasonable possibility, should be reported to Global Pharmacovigilance department and will not be recorded in the clinical database.

Serious adverse events and adverse events of special interest (AESI) are defined in the protocol (refer to protocol Section 10.5.1.2 and 10.5.1.3). AESI will be identified and summarized based on CRF information, not standardized or customized MedDRA queries.

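### Protocol 10.5.2 ends adverse event recording at the last dose for an undefined group of early terminators, against other protocol sections and the SAP, which collect or analyse events after that dose

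*Protocol*

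**What the plan says.** The instruction on what goes on the case report form is the second bullet of protocol 10.5.2. Adverse events (AEs) from consent "until the end of study visit, or the last IMP administration for patient with early termination, are to be recorded". Patients with early termination therefore have an earlier cut-off than everyone else. The protocol does not define the term.

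Other protocol text on the same patients:

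- 10.5.2, later bullet: "When treatment is prematurely discontinued, the patient's observations will continue until the end of the study visit", unless the patient is lost to follow-up.
- 10.4.3, on handling after permanent discontinuation of drug: "Patients will be followed-up according to the study procedures as specified in this protocol up to the scheduled date of study completion", or until any AE under follow-up has recovered or stabilized, whichever is later.
- 7.3: patients who discontinue or withdraw "will be contacted in order to obtain information about the reason(s) for discontinuation/withdrawal and for collection of AEs, if any".
- 10.2.5.1: AEs are a listed assessment at the discontinuation/withdrawal visit. Footnote f of the flow chart in 1.2 says of eliglustat administration: "Only at Study completion visit and not at Patient discontinuation/withdrawal visit". The withdrawal visit is thus off drug.

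The SAP says:

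- 2.1.4.1: AEs "will be recorded from the time of signed informed consent until the end of the study", with no exception for early termination.
- 2.1.4: the treatment-emergent period is "the time from the first administration of the IMP to the last administration of the IMP + 5 days". A post-treatment period follows it.
- 2.4.5.1: an overview and a by-patient listing of post-treatment AEs are planned.

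Protocol 11.4.3 ends the treatment-emergent window at the last dose. SAP 1.6 reports its own definition of the treatment-emergent period as a clarification. It does not address the recording rule.

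**The concern.** The SAP can analyse only what sites enter. The 10.5.2 bullet is the sentence a site would consult to decide whether a new event belongs on the form, and for early terminators it says to stop at the last dose. Elsewhere the plan assumes that such events are collected and gives them two places in the analysis, the 5-day residual period and the post-treatment summary.

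The study has one arm, approximately 32 patients, approximately 4 sites and no Data Monitoring Committee. If sites follow different sentences, the post-treatment AE overview and the tables of AEs leading to death would depend on which sentence each site chose. Nothing in the output would show it.

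**Working it through.** The plan states no figure on this point to reproduce. The check sets the collection windows side by side and then works out the length of the gap.

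**Step 1. End of AE collection for a patient who stops early**

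| Source | End of collection or observation |
|---|---|
| Protocol 10.5.2, recording bullet | Last dose |
| Protocol 10.5.2, later bullet | Patient's end-of-study visit (refers to observations, without naming AE recording) |
| Protocol 10.4.3 | Scheduled completion, or AE recovery/stabilization if later |
| Protocol 7.3 and 10.2.5.1 | Contact and visit at discontinuation/withdrawal, off drug |
| SAP 2.1.4.1 | End of the study |
| SAP 2.1.4, treatment-emergent | Last dose + 5 days |
| SAP 2.4.5.1, post-treatment | After last dose + 5 days |

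**Step 2. Does a charitable reading remove the conflict?** Suppose early termination means leaving the study, so that the later bullet and 10.4.3 govern patients who stop drug but stay. A last-dose cut-off still excludes new events found at the off-drug withdrawal visit, where 7.3 and 10.2.5.1 require AE collection. It also excludes the SAP's 5-day residual period. The conflict is smaller but remains.

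**Step 3. Length of the gap for one patient, if a site applies the recording bullet**

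Recorded time for new events after the last dose = 0 days.

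- Early termination means leaving the study: the gap is the 5-day residual period and the interval to the withdrawal visit.
- Early termination includes stopping drug but staying: gap = visit week − stopping week. The documents give no stopping times, so those below are assumptions.

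| Assumed stop | Gap to Week 104 | Gap to Week 208 |
|---|---|---|
| Week 26 | 104 − 26 = 78 weeks | 208 − 26 = 182 weeks |
| Week 52 | 104 − 52 = 52 weeks | 208 − 52 = 156 weeks |
| Week 78 | 104 − 78 = 26 weeks | 208 − 78 = 130 weeks |

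**Step 4. Which events are exposed?** Under 10.5.2, AEs already present are followed to recovery or stabilization. Under 10.5.3, SAEs judged related remain reportable after the end of study, although SAP 2.1.4.1 keeps them out of the clinical database. What remains exposed is new AEs starting after the last dose.

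**Step 5. Which outputs are affected?** Completers take their last dose at the last visit (protocol synopsis and footnote f), which is also when 10.5.2 ends their recording. Early terminators are therefore almost the only source of new residual-period or post-treatment events. If every site applied the recording bullet, those outputs would receive essentially no new-onset events.

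**The case against.** The strongest reply is that this is a drafting slip inside a plan whose intent is clear. Protocol 7.3, 10.2.5.1, 10.4.3, the later bullet of 10.5.2 and the flow chart's continuous AE monitoring, with contact about every 4 weeks, all point to continued collection. SAP 2.1.4.3 mentions early termination as an occasion for blood sampling, alongside visits, which fits leaving the study. On that reading patients who stop drug but stay have no gap. SAP 2.4.5.1 also puts its focus on treatment-emergent events and describes post-treatment events separately. Most of this stands: loss is conditional on a site applying one half-sentence over the rest, and the long gaps depend on one reading of an undefined term. It does not remove the conflict that Step 2 leaves.

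A reader might go further and infer that events are lost in the patients most likely to have them, so that the safety profile looks better than it is. The removal reasons in 7.3, such as an intolerable AE or a decline in Gaucher disease, make such selection plausible. But the documents give neither a discontinuation rate nor an off-drug event rate. Patients enter after about 4 to 8 years on eliglustat, and the protocol introduction says that few discontinued for AEs.

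A patient-year figure is also tempting, but it rests on invented inputs. If 3 to 6 of 32 patients stopped at Week 52 and all stayed to Week 104, the gap would be 3/64 = 4.7% to 6/64 = 9.4% of two-year patient time. Nearly all of that lies outside the treatment-emergent window. The part inside is 3 × 5 = 15 to 6 × 5 = 30 days, or 0.04 to 0.08 patient-years, which is 0.06% to 0.13% of 64.

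The count of deaths is less exposed. Protocol 11.4.3 refers to a death report form, and 10.4.4 seeks vital status for patients who do not return. The tables of AEs leading to death do rely on the AE page.

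**Conclusion.** The contradiction is real and survives the most favourable reading of early termination. If a site applies the recording bullet, new-onset AEs after the last dose are not entered for early terminators. The minimum gap is the SAP's 5-day residual period and the time to the withdrawal visit. If the term includes patients who stop drug but remain in the study, the gap is all of their off-drug follow-up.

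The number of events at stake cannot be computed from the documents, and neither certain loss nor a favourable bias is shown. The main effect falls on the post-treatment summary, with a small effect on the treatment-emergent counts. It is worth correcting because the rule addresses sites directly and events that were never entered cannot be recovered at analysis.

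**What to change.** In protocol 10.5.2, replace the last-dose exception with one recording end point. AEs are recorded from consent to the patient's end-of-study visit, including for patients who stop eliglustat but remain in the study. For patients who leave the study, they are recorded to the discontinuation/withdrawal visit and at least to 5 days after the last dose where the patient can be contacted. Deleting the phrase alone is not enough, because it leaves no stated end for patients who leave.

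In the same change:

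- Define early termination as of treatment or of study, and use it consistently.
- Align the treatment-emergent window in protocol 11.4.3 with the SAP's last dose + 5 days.
- Keep the SAP's separate treatment-emergent and post-treatment summaries, so that off-drug events are shown apart.

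The cost is a short wording change in the protocol and a few more AE pages for patients who are already being contacted.
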